#### Figure 1. Study Design

#### 3.1.1 Study population

Data will be collected for all eligible adult COVID-19 patients who have been prescribed nirmatrelvir, ritonavir across 3 selected sites in KSA which are National Guard Hospital-Riyadh, King Faisal Specialist Hospital-Riyadh and King Faisal Specialist Hospital-Jeddah. These 3 healthcare centers are the largest COVID-19 care providers in KSA representing the majority of COVID-19 patients who have been prescribed nirmatrelvir, ritonavir at the national level. In addition, these three healthcare centers have the same guidelines for treatment and management of patients with COVID-19.

The selected sites with well-established clinical research infrastructures, are situated in the major cities of KSA, where COVID-19 patients are most prevalent. They provide medical attention to any COVID-19 patient and provide healthcare to complicated patients, including immunocompromised patients.

These facilities also maintain patient records and have access to electronic medical records for patient data retrieval.

The minimum target sample size is 250 patients. Patient eligibility will be assessed at patient index date. Patients in Cohort 1 will be identified during a 15-month lookback period prior to the date of site initiation, and patients in Cohort 2 will be identified

PFIZER CONFIDENTIAL CT24-WI-GL03-RF03 2.0 Non-Interventional Statistical Analysis Plan 01-Jun-2020 Page 11 of 42 following the date of site initiation if the minimum target sample size for the study is not achieved from Cohort 1.

#### 3.1.2 Inclusion Criteria

Patients must meet all of the following inclusion criteria to be eligible for inclusion in the study:

- 1. Confirmed COVID-19 infection during the study observation period.
- 2. Age  $\geq 18$  years old.
- 3. Nirmatrelvir, ritonavir written prescription.

#### 3.1.3 Exclusion Criteria

There are no exclusion criteria for this study.

#### 3.1.4 Data source

*This is an observational, non-interventional study (NIS) involving retrospective collection of data throughout the observation period, obtained from the source outlined below.* 

• Medical records of patients prescribed nirmatrelvir; ritonavir: The authorized physician or study investigator will record patient demographics, clinical characteristics, COVID-19 vaccination history, nirmatrelvir, ritonavir prescription data, and HCRU data from patients' medical records into an eCRF.

All data collected in this study are intended to capture COVID-19 patient demographics, clinical characteristics, and patients' HCRU in a real-world setting. An eCRF will primarily be used for data collection, located on a secure web-based electronic data capture (EDC) system. The use of a standardised eCRF will ensure data is captured consistently across all sites. The eCRF must be signed by the investigator, and the signature serves to attest that the information contained in the eCRF is true. At all times, the investigator has the final responsibility for the accuracy and authenticity of all clinical and laboratory data entered into the eCRFs.

*Table 1 below depicts the data collection schedule for the study.* 

Variables	(	Cohort 1	(	Cohort 2
	Index date a	During the 30-day post-index period b	Index date a	During the 30-day post-index period c
Patient demographics	X		X	
Patient clinical characteristics	X		X	
COVID-19 vaccination history	X		X	
COVID-19 infection data	X	X	X	Х
Nirmatrelvir, ritonavir prescription data	X		X	
HCRU data	X	X	X	X

#### Table 1.Data Collection Schedule

COVID-19: Corona Virus Disease 2019 caused by SARS-CoV-2; HCRU: Healthcare Resource Use.

a Cohort 1/Cohort 2: Index date is defined as the date of nirmatrelvir, ritonavir prescription.

b Cohort 1: Post-index period is defined as the 30-day period after the index date and prior to the site initiation date.

*c* Cohort 2: Post-index period is defined as the 30-day period after the index date and after the site initiation date.

#### 3.1.5 Patient Medical Records

The authorized physician or study investigator will record patient demographics, clinical characteristics, COVID-19 vaccination history, nirmatrelvir, ritonavir prescription data, and HCRU data from patients' medical records into an eCRF.

#### 3.2 STUDY OBJECTIVES

The aim of this study is to describe the baseline demographic, clinical characteristics, and HCRU of adult ( $\geq$ 18 years) COVID-19 patients who have been prescribed nirmatrelvir, ritonavir treatment.

#### 3.2.1 Primary objective:

To describe the baseline demographic and clinical characteristics, including preexisting comorbidities, of adult COVID-19 patients who have been prescribed nirmatrelvir, ritonavir treatment.

#### 3.2.2 Secondary objective:

*To assess adult COVID-19 patients' HCRU within the 30-day period following nirmatrelvir, ritonavir prescription, including:* 

• Overall HCRU in inpatient and outpatient settings.

#### 4 ANALYSIS SETS/POPULATIONS

#### 4.1 FULL ANALYSIS SET

The Full Analysis Set will contain all patient's data who fulfil the eligibility criteria (*see* Section 2.1.2).

#### 4.2 SUBGROUPS

*Exploratory stratifications will be conducted, as appropriate and where the sample size permits, to explore differences by:* 

- *Age groups: 18–49, 50–64, 65–74, ≥75 years of age;*
- Gender;
- *BMI categories:* (<18.5 = underweight, 18.5−24.9 = normal, 25−29.9 = overweight, ≥30 = obese);
- *Smoking status;*
- *Medications used to treat COVID-19 in addition to nirmatrelvir, ritonavir;*
- *Previous COVID-19 infection;*
- COVID-19 vaccination history;
- *Nirmatrelvir, ritonavir treatment completion (if available)*
- Days from COVID-19 diagnosis to nirmatrelvir, ritonavir index date;
- Days from prescription to dispensing (if available).
- Days from COVID 19 symptoms onset to dispensing (if available).
- Days from COVID 19 symptoms onset to nirmatrelvir, ritonavir prescription (if available).

For each stratification variable, the full analysis set will be segmented into nonoverlapping subgroups based on the stratification variable values. The stratifications may not be meaningful, if there are no patient's data in some of the groups or there are many variables with a lot of missing data.

The exploratory stratifications will be conducted for the following study objectives if enough data are available:

# Secondary objective: To assess adult COVID-19 patients' HCRU within the 30-day period following nirmatrelvir, ritonavir prescription, including: Overall HCRU in inpatient and outpatient settings.

The specific stratifications, and their corresponding reporting labels will be the following:

• Age groups: Age at time of PAXLOVID™ prescription will be further categorized into 18–49, 50–64, 65–74, ≥75 years. Descriptive summary tables for subgroup analysis by defined age groups for the specified study objectives will be created as shown in *Table Shells 10*.

PFIZER CONFIDENTIAL CT24-WI-GL03-RF03 2.0 Non-Interventional Statistical Analysis Plan 01-Jun-2020 Page 14 of 42 *Gender (Male, Female);* Descriptive summary tables for subgroup analysis by gender for the specified study objectives will be created as shown in *Table Shells* 11

- *BMI categories:* Body Mass Index (BMI) at time of PAXLOVID™ prescription will be further categorized as <18.5 = underweight, 18.5–24.9 = normal, 25–29.9 = overweight, ≥30 = obese. Descriptive summary tables for subgroup analysis by defined BMI categorization for the specified study objectives will be reported as shown in *Table Shells 12*.
- *Smoking status (*Never smoker; Former smoker; Current smoker); Descriptive summary tables for subgroup analysis by smoking status in terms of never smoker, former smoker and current smoker for the specified study objectives will be reported as shown in *Table Shells 13*.
- Medications used to treat COVID-19 in addition to nirmatrelvir, ritonavir; Descriptive summary tables for subgroup analysis by Medications used to treat COVID-19 in addition to nirmatrelvir, ritonavir at time of PAXLOVIDTM prescription for the specified study objectives will be reported as shown in *Table Shells 14.*
- *Previous COVID-19 infection (Yes, No);* Descriptive summary tables for subgroup analysis by Previous COVID-19 infection for the specified study objectives will be created as shown in *Table Shells 15.* Additionally, Number of previous COVID-19 infections before the index date will be reported and further stratified by 0, 1, 2 and more. Descriptive summary tables for these groups will be reported as shown in *Table Shell 15.1* (If sufficient data available).
- *COVID-19 vaccination history;* Descriptive summary tables for subgroup analysis by COVID-19 vaccination history for the specified study objectives will be reported as shown in *Table Shells 16.*
- *Days from COVID-19 diagnosis to nirmatrelvir, ritonavir index date;* Duration in days from COVID-19 diagnosis to nirmatrelvir, ritonavir index date will be further categorized as 0-2 days, 3-5 days, more than/equal to 6 days. Descriptive summary tables for subgroup analysis by defined duration categorization for the specified study objectives will be reported as shown in *Table Shells 17*.
- *Days from prescription to dispensing (if available):* Duration in days from prescription to dispensing will be further categorized as 0-2 days, 3-5 days, more than/equal to 6 days. Descriptive summary tables for subgroup analysis by defined duration categorization for the specified study objectives will be reported as shown in Table Shells *Table Shells 18.*

PFIZER CONFIDENTIAL CT24-WI-GL03-RF03 2.0 Non-Interventional Statistical Analysis Plan 01-Jun-2020 Page 15 of 42

- Days from COVID 19 symptoms onset to dispensing (if available): Duration in days from COVID 19 symptoms onset to dispensing as 0-2 days, 3-5 days, more than/equal to 6 days. Descriptive summary tables for subgroup analysis by defined duration categorization for the specified study objectives will be reported as shown in Table Shells **Table Shells 19**.
- Days from COVID 19 symptoms onset to nirmatrelvir, ritonavir prescription (if available): Duration in days from COVID 19 symptoms onset to prescription as 0-2 days, 3-5 days, more than/equal to 6 days. Descriptive summary tables for subgroup analysis by defined duration categorization for the specified study objectives will be reported as shown in Table Shells *Table Shells 20*.

Additionally, the exploratory stratifications will be conducted for COVID-19 variant and Duration to COVID-19 negative result(s) if enough data are available and will be reported as shown in Table Shells *Table Shells 22.1 to 22.7* and *Table Shells 23.1 to 23.10* respectively.

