#### Cohort 1:

The study will involve collection of pre-defined, structured data retrospectively from medical records (electronic and/or paper if necessary) of patients who meet the study eligibility criteria (see Section 3.1.2) and who have been prescribed nirmatrelvir, ritonavir treatment within a 15-month lookback period from the date of site initiation (Cohort 1). The lookback period will span from 01 April 2022 to 30 June 2023. Data abstracted from patients' medical records will include patient demographics and clinical characteristics at index date (defined as the date of nirmatrelvir, ritonavir treatment prescribing), in addition to patients' HCRU during the 30-day period post-index date.

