# Secondary analysis: To assess adult COVID-19 patients' HCRU within the 30-day period following nirmatrelvir, ritonavir prescription, including: Overall HCRU in inpatient and outpatient settings.

Healthcare Resource Use (HCRU) data will be summarized using descriptive statistics in terms of patient hospitalization, number of time patient hospitalization, cause of patient hospitalization, length of stay in the hospitalization, Intensive Care Unit (ICU) admission,

PFIZER CONFIDENTIAL CT24-WI-GL03-RF03 2.0 Non-Interventional Statistical Analysis Plan 01-Jun-2020 Page 19 of 42 number of Intensive Care Unit (ICU) admission, length of stay in Intensive Care Unit (ICU), supplemental oxygen use, type of oxygen, vasopressor use, patient intubation, outpatient visits, number of outpatient visits and reason of outpatient visits during the 30 days post index date and reported as shown in the *Table Shell 9*. Further stratification will be performed as described in section 3.2.

COVID-19 PCR and /antigen test result(s), Result(s) by PCR only, Result(s) by antigen test only, duration to COVID-19 negative result(s) by PCR and/antigen tests from the index date will be reported will be reported as shown in the *Table shell 21*.

COVID-19 variant by following stratifications will be reported as shown in the *Table shell 22.1 to 22.7: (if sample size permits)* 

- Age groups: *Table shell 22.1*
- Gender: *Table shell 22.2*
- BMI categories: *Table shell 22.3*
- Smoking status: *Table shell 22.4*
- Previous COVID-19 infection: *Table shell 22.5*
- COVID-19 vaccination history: Table shell 22.6
- Underlying medical conditions: Table shell 22.7

Duration to COVID-19 negative result(s) by following stratifications will be reported as shown in the *Table shell 23.1 to 23.10: (if sample size permits)* 

- Age groups: *Table shell 23.1*
- Gender: *Table shell 23.2*
- BMI categories: *Table shell 23.3*
- Smoking status: *Table shell 23.4*
- Previous COVID-19 infection: *Table shell 23.5*
- COVID-19 vaccination history: *Table shell 23.6*
- Underlying medical conditions: Table shell 23.7
- Medications used to treat COVID-19 in addition to nirmatrelvir, ritonavir: *Table shell 23.8*
- Days from COVID-19 diagnosis to nirmatrelvir, ritonavir index date: *Table shell* 23.9
- Days from prescription to dispensing (*if available*): *Table shell 23.10*

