Frequency	Nirmatrelvir, ritonavir prescription data	At index date	Frequency of Nirmatrelvir/Ritonavir will be reported as: • Twice a day • Other • If Other, Specify (Open field)
Dispensed amount	Nirmatrelvir, ritonavir prescription data	At index date	Open field: Will be captured by Box, Blister and Tablets.
Dispensed date (if available)	Nirmatrelvir, ritonavir prescription data	At index date	Date of dispensed will be captured in (DD-MM-YYYY)
Days from COVID-19 diagnosis to nirmatrelvir, ritonavir prescription date	Nirmatrelvir, ritonavir prescription data	At index date	Days from COVID-19 diagnosis to nirmatrelvir, ritonavir index date will be calculated as: [Prescription date (Index date)- Date of COVID-19 diagnosis]
Days from COVID-19 diagnosis to nirmatrelvir, ritonavir prescription date (Categories)	Nirmatrelvir, ritonavir prescription data	At index date	Days from COVID-19 diagnosis to nirmatrelvir, ritonavir index date will be categorized as: • 0-2 days • 3-5 days • $\geq 6$ days
Days from prescription to dispensing	Nirmatrelvir, ritonavir prescription data	At index date	Days from prescription to dispensing will be calculated as: [Dispensed date- Prescription date (Index date)]
Days from prescription to dispensing (Categories)	Nirmatrelvir, ritonavir prescription data	At index date	Days from prescription to dispensing will be categorized as: • 0-2 days • 3-5 days

Variables	Role	Time point(s)	Operational definition
			• $\geq 6$ days
Days from COVID 19 symptoms onset to dispensing (if available)	Nirmatrelvir, ritonavir prescription data	At index date	Days from COVID 19 symptoms onset to dispensing will be calculated as: [Dispensed date- COVID-19 symptoms onset date]
Days from COVID 19 symptoms onset to dispensing (Categories)	Nirmatrelvir, ritonavir prescription data	At index date	Days from COVID 19 symptoms onset to dispensing will be categorized as: • 0-2 days • 3-5 days • ≥ 6 days
Days from COVID 19 symptoms onset to nirmatrelvir, ritonavir prescription (if available)	Nirmatrelvir, ritonavir prescription data	At index date	
 
Days from COVID 19 symptoms onset to nirmatrelvir, ritonavir prescription will be calculated as:
 
[Prescription date (Index date) COVID-19 symptoms onset date]
 

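### Dispensing-delay strata (shells 18 and 23.10, and part of shell 19) are fixed after index, so differences across them can arise with no effect of dispensing time

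*SAP*

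**What the plan says.** **Time zero.** Under SAP Table 1, "Index date is defined as the date of nirmatrelvir, ritonavir prescription". SAP 3.1 collects "patients' HCRU during the 30-day period post-index date", and SAP 7.2 reports "duration to COVID-19 negative result(s) by PCR and/antigen tests from the index date". Both outcomes therefore start at prescription.

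**Strata.** For shell 18, SAP 4.2 says: "Duration in days from prescription to dispensing will be further categorized as 0-2 days, 3-5 days, more than/equal to 6 days". For shell 19 it says: "Duration in days from COVID 19 symptoms onset to dispensing as 0-2 days, 3-5 days, more than/equal to 6 days". In SAP 7.2, shell 23.10 breaks time to negative down by "Days from prescription to dispensing". Annex Table 2 (SAP 11.1) computes the prescription-to-dispensing delay as dispensed date minus prescription date and gives the index date as its time point.

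**Purpose and safeguards.** SAP 4.2 says the strata serve to look at differences, if sample size allows, and uses dispensing dates only if available. SAP 7.1 plans no testing of these tables. Eligibility (SAP 3.1.2 and 3.1.3) needs a prescription, not dispensing, and nobody is excluded. SAP 6 tabulates missing categories as a category. SAP 7 contains no landmark for these tables, and the limitations in SAP 8 do not mention the issue.

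**The concern.** A stratifier can be read like a baseline variable only if it is known when follow-up starts. Here it is not. While a patient waits for dispensing, the outcome clock is already running, and an admission or a negative test in that interval may change whether and when the drug is dispensed. The strata then sort patients partly by their early outcome.

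The stake is how the tables will be read. The SAP background says treatment should begin within 5 days of symptom onset and cites a study with better prognosis after early initiation. A table of hospitalisation or time to negative by 0–2, 3–5 and ≥6 days will be taken as evidence on timing. Leaving out a p-value does not correct how patients were allocated to the rows.

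**Working it through.** There is no plan figure to reproduce. The tables are descriptive, and the target of about 250 patients (SAP 3.1) rests on feasibility.

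**1. When is each stratifier known?**
- Shell 17 (diagnosis to prescription) and shell 20 (onset to prescription): both end at index, so known at time zero.
- Shells 18 and 23.10 (prescription to dispensing): any value above 0 is fixed after time zero.
- Shell 19 (onset to dispensing): the sum of a pre-index part (onset to prescription) and a post-index part (prescription to dispensing). A patient prescribed on day 6 after onset and dispensed the same day falls in ≥6 days with no post-index wait.

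**2. HCRU, closed form.** Assume no effect of dispensing time, and that an admission before dispensing cancels it. With 30-day risk R and risk R6 by day 6, a group dispensed on day 6 has risk (R − R6)/(1 − R6); a group dispensed on day 0 has risk R. At an assumed R = 10%:
- constant hazard: R6 = 1 − 0.9^(6/30) = 2.09%, giving (0.10 − 0.0209)/0.9791 = 8.08%, ratio 0.81;
- 35% of events before day 6: (0.10 − 0.035)/0.965 = 6.74%, ratio 0.67;
- 50% before day 6: (0.10 − 0.05)/0.95 = 5.26%, ratio 0.53.

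**3. HCRU, simulation.** This used 2,000,000 patients per scenario and no true effect. Assumed delays were 0–8 days (65% in 0–2, 20% in 3–5, 15% in ≥6), with constant or front-loaded hazard (Weibull shape 0.7). The table shows 30-day admission at R = 10%, 0–2 days v ≥6 days; the last column is the range of ratios over R = 5%, 10% and 20% and both hazards.

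| Assumed link | Constant hazard | Front-loaded | Ratio range |
|---|---|---|---|
| Admission cancels dispensing | 9.81% v 7.86% | 9.54% v 6.56% | 0.68–0.80 |
| Admission triggers dispensing | 10.48% v 8.14% | 10.96% v 6.85% | 0.62–0.78 |
| No link | 9.98% v 10.06% | 9.97% v 9.99% | 1.00–1.02 (noise) |
| Admission delays dispensing by 3 days | 9.81% v 11.61% | 9.54% v 12.85% | 1.16–1.35 |

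**4. Time to negative, simulation.** Weibull shape 2, no true effect, same delays. If patients are dispensed only while still positive, the median days from index (0–2 v ≥6) are 5.1 v 8.4, 8.1 v 10.5 and 10.0 v 12.1, for overall medians of 5, 8 and 10. If dispensing is unrelated to the test result, the medians do not differ.

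Restarting the clock at dispensing does not cure this. At an overall median of 8, the medians from dispensing are 7.5 v 3.7 days.

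**5. Landmark.** Among patients event-free at day 8 (the longest assumed delay), counting events from day 8 to day 30 under constant hazard, the late/early ratios were 0.996, 1.001 and 0.995 at R = 5%, 10% and 20%. The artefact disappears because no earlier event can have altered dispensing in these patients. The same reasoning covers a day-6 landmark: status by day 5 is settled before any counted event. The day-6 version was not itself simulated.

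**The case against.** The strongest reply has four parts.

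*Direction.* A reader might infer classic immortal time: that the ≥6-day group is event-free for 6 of 30 days by construction, so late dispensing must look protective. The documents do not support that. No passage says admission stops, triggers or delays dispensing, and patients already in hospital at index are not excluded. Nor does an outpatient or ER visit by itself rule out later dispensing. A reader might also carry the protective direction over to shell 23.10, where the plausible artefact runs the other way. Both corrections stand.

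*Who is lost.* A reader might assume that patients without a dispensing date drop out. SAP 6 keeps them as a missing category. What remains is that this category mixes never-dispensed patients with unrecorded dates.

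*Feasibility.* A landmark for HCRU needs event dates. Protocol Table 3 and Annex Table 2 list yes/no, cause and length of stay, with no admission or visit dates. Planned data collection ended on 01 February 2024 (Protocol 6), and SAP 2.0 of 16 September 2024 refers to analysis already performed. This stands for shells 18 and 19. It does not apply to shell 23.10, because dispensing and test dates are listed.

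*Materiality.* The tables are exploratory, untested and conditional on data, and no objective concerns effectiveness. If 10% of 250 patients were late, that is 25 patients; 2 admissions among 25 has an exact 95% interval of about 1% to 26%. So a distorted ratio may well be lost in noise. That lowers the priority but does not make the comparison interpretable.

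**Conclusion.** The point holds in a limited form. Shells 18 and 23.10, and the prescription-to-dispensing part of shell 19, group outcomes counted from prescription by a delay known only afterwards. Annex Table 2 mislabels that delay as an index-date variable, and the SAP gives no safeguard or caution.

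Differences across these strata can arise with no effect of dispensing time. For HCRU the sign is uncertain: the simulated late/early ratio ran from 0.62 to 1.35 depending on the assumed link between admission and dispensing, and the closed form fell to 0.51 (R = 5%, half of events before day 6). For time to negative, late groups will tend to look slower if patients are dispensed only while still positive, by 10.5 − 8.1 = 2.4 days in the middle scenario.

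Every size here rests on assumed event rates, event timing and delays. The documents give none of these, so the actual size is unknown. Shells 17 and 20 are unaffected.

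**What to change.** 1. **Shells 17 and 20.** Name these, whose stratifiers are known at index, as the timing stratifications from which differences are described. Both are already planned.
2. **Shell 23.10.** Use a day-6 landmark. Among patients not yet negative at day 6, classify as dispensed day 0–2, dispensed day 3–5 or not dispensed by day 5. Count time to negative from day 6, and list earlier negatives in a separate row. The dates needed are already listed variables.
3. **Shells 18 and 19.** Check whether the eCRF holds admission and visit dates. If it does, apply the same landmark to HCRU. If not, report both shells without comparison across strata, with a note that the strata are defined after index. Keep shell 19's own onset-to-dispensing stratifier; do not replace it with shell 18's.
4. **Annex Table 2 and missing dates.** Correct the index-date time point for the dispensing delays. Where records allow, report never-dispensed patients apart from unrecorded dispensing dates, so that the not-dispensed-by-day-5 row does not absorb missing data.

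Cost: a short SAP edit, a label change and modest programming for shell 23.10. Shells 18 and 19 need only a footnote unless event dates turn out to exist. The downside is that events in days 0–5 are left out of the landmarked rows, and these tables support fewer statements about dispensing delay. The landmark removes the time-zero artefact only; patients dispensed late may still differ in other ways.
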